The study design will be a randomized, double-blind, placebo-controlled trial. Following satisfaction of inclusion/exclusion criteria and enrollment into the study, designated pharmacy staff will be notified of the patient's enrollment and scheduled timing of surgery. Designated pharmacy staff will randomize the patient and assign the patient a unique study number. The subject will be randomized based on a predetermined algorithm by the pharmacy staff to receive preoperative intravenous tranexamic acid or preoperative intravenous isotonic electrolyte solution as placebo. The preparation will be indistinguishable by nursing, surgical, or anesthesia staff. The tranexamic acid group will receive a 1000 mg dose immediately preceding surgery, administered by the anesthesiologist. Both the tranexamic acid and placebo will be administered via intravenous piggyback over 15 minutes. Standard daily

laboratory measurements will continue unless clinical conditions necessitate more frequent monitoring. Transfusion will take place for hemoglobin levels < 7.0 g/dL or hemoglobin level < 10 g/dL with clinical symptoms indicating need for transfusion, per standard practice. Final decision on transfusion will be made according to the staff surgical oncologist's discretion.

Data to be recorded from operative records will include operative blood loss, operative time, amount of fluid received, and intraoperative transfusion requirements. Postoperative data including hemoglobin levels, transfusion requirements, surgical complications, thromboembolic events, length of ICU stay, length of hospital stay, and cost of inpatient stay. Subjects will be followed for 90 days postoperatively. Additionally, re-admission to the hospital during this time will also be recorded with associated complications.

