**e. Data Management**

The study personnel will collect outcome data on a weekly basis. Data will be stored in a password-protected file for security. Pharmacy staff will keep a secure record of subjects randomized to the tranexamic acid and placebo arms respectively, which will be blinded from the study personnel.

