**f. Provisions to Monitor the Data for the Safety of Subjects**

Adverse events including thromboembolic events and development of acute renal failure will be monitored and recorded on a weekly basis by study personnel. In the event an increased number of unanticipated events occur, the study will be temporarily stopped pending review. Review of unblinded data will be performed by an independent clinician, pharmacist, and statistician to determine the need to discontinue or resume the study. If a significant increase in adverse events is noted in the treatment arm, the trial will be terminated. Decisions resulting from the review will be discussed with the primary investigator.

Interim reviews of unblinded data for statistically significant findings will be performed by an independent clinician, pharmacist, and statistician after every 50 subjects complete the study. Findings will be reviewed with the investigators, and decisions will be made as to whether or not the research study continues. These interim reviews and outcomes will be reported to the IRB.

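### Section 8f has findings from the unblinded interim reviews reviewed with the investigators, and nothing limits what is passed on to a recommendation to continue or stop

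*Combined protocol and SAP*

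**What the plan says.** Section 8d sets the design: "The study design will be a randomized, double-blind, placebo-controlled trial". Section 8f describes two kinds of review by people outside the study team.

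- **Scheduled interim reviews**, after each further 50 completed subjects: "Interim reviews of unblinded data for statistically significant findings will be performed by an independent clinician, pharmacist, and statistician". The next sentence is: "Findings will be reviewed with the investigators, and decisions will be made as to whether or not the research study continues". It is followed by: "These interim reviews and outcomes will be reported to the IRB".
- **A safety review**, triggered by an increased number of unanticipated events. Its closing sentence is: "Decisions resulting from the review will be discussed with the primary investigator".

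Section 8e deals with blinding of the allocation list, which the pharmacy keeps and "which will be blinded from the study personnel". The same section says of those personnel: "The study personnel will collect outcome data on a weekly basis". Section 13 adds that identifiable data and the pharmacy's randomization record are stored securely. Section 8a makes the total of 200 subjects depend on what the interim analyses show.

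**The concern.** Independent reviewers protect a blinded trial only as far as the comparative results stay with them. Here the reviewers are independent, but what they find is then reviewed with the investigators, in the same sentence as the decision on whether to go on. If *findings* includes a comparison of the arms, the investigators would learn of a trend while subjects are still being recruited and followed.

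What is at stake is the confidentiality of interim results. Someone who knows that one arm appears to be ahead may recruit differently, or may weigh the question of continuing differently, without intending to. Knowing a trend is not the same as knowing which treatment a particular subject received, so the blind at subject level is not what is at risk.

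**Working it through.** The plan gives no figure on this point to reproduce. The check is to set the relevant sections side by side and ask whether any of them closes the gap.

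1. **What is passed on.** The interim sentence in 8f passes on findings and mentions the decision about continuing separately. The safety-review sentence in the same section passes on decisions. The difference in wording supports reading the first as broader than the second, but does not prove it.

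2. **To whom.** Findings go to the investigators as a group. The sentence does not say who then takes the decision.

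3. **Whether another section limits it.**
   - 8e withholds the list of who received what. It does not mention interim comparisons.
   - 13 covers storage of identifiable data and of the randomization record. It does not mention interim results either.
   - The IRB sentence in 8f adds a recipient. It sets no limit on what the investigators see.
   - 8d has indistinguishable preparations, which hides individual allocation. It does not hide a summary by arm.

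   No section confines the communication to a recommendation.

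4. **Whether enrolment is still open at the looks.** This is a check on timing only and does not measure harm.
   - Inputs: 200 subjects (8a and 9a), a look after each 50 completers (8f), 90 days of follow-up (8d), and about 15 eligible types of surgery a month (section 7).
   - Assumptions: completing the study means completing 90 days, accrual is steady, and the review takes no time. Using 15 a month also assumes that every surgery is enrolled, so it is the fastest case.
   - Subjects enrolled but still in follow-up at a look: 15 × 90/30.44 = 15 × 2.957 ≈ 44.
   - Still to be enrolled at look k: 200 − 50k − 44, that is about 106, 56 and 6 at looks 1, 2 and 3.
   - As accrual slows, the number in follow-up falls towards zero and these figures approach 150, 100 and 50.

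   Enrolment is therefore clearly open at the first two looks. At the third it may be nearly finished if accrual is at its fastest.

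5. **Size of the effect.** Nothing in the documents says how far knowledge of a trend would change anyone's behaviour, so no bias can be computed.

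**The case against.** The strongest reply is that this is an ambiguity and not a stated defect. The reviewers look for statistically significant findings and the next sentence begins with the word *Findings*, so the natural reference may be only to whether such a result exists. On that reading, a look that finds nothing tells the investigators little more than a recommendation to continue would. This stands as a possible reading. It does not remove the point, because the broader reading is equally compatible with the text and a team following the protocol could share results by arm without deviating from it.

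The routes by which a known trend could act are also narrow. The exclusion left to the investigator's judgement (8b) concerns conditions that interfere with consent, cooperation or participation. Removal by the primary investigator (8g) is tied to the subject's best interest. Section 7 says that everyone eligible will be recruited, research staff obtain consent, and the pharmacy randomizes after enrolment. All of this stands and limits how much weight the concern can bear.

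Three stronger inferences are tempting, and the documents do not support them.

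- **That the investigators will be shown results by arm.** The text allows it but does not say it.
- **That the comparison will be biased, for example through the surgeon's final say on transfusion (8d).** The documents do not say that the investigators are the treating surgeons. Without individual allocation, a change in practice would act on both arms. A bias between arms would also need the arm to be guessed.
- **That the event-triggered safety review has the same fault.** Its sentence already passes on decisions, which is close to the limit asked for here. Its silence about the underlying data is not a rule to share them.

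**Conclusion.** The point holds as a gap in the confidentiality of interim results. Section 8f states a rule under which findings from unblinded reviews reach the investigators of a double-blind trial, and no section restricts what those findings may contain. Knowledge of a trend could affect trial conduct and the continuation decision.

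No bias between the arms is shown, and the size of any effect cannot be computed. The conclusion rests on the wording alone. It assumes only that *findings* may be read to include comparative results, and that at least some looks fall while enrolment is open, which the timing check supports for the first two looks even at the fastest accrual. It is a cheap improvement.

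**What to change.** Replace the interim sentence in 8f with:

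> After each interim review the independent clinician, pharmacist and statistician will give the investigators only a recommendation to continue or stop; comparative results will be kept from the investigators and study personnel until follow-up of enrolled subjects is complete, unless the independent reviewers or the IRB judge disclosure necessary for subject safety, and any comparative results reported to the IRB will go directly from the independent reviewers.

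The safety-review sentence needs no change. Neither the present sentence nor this one names who takes the decision to continue, and the sponsor could name that person or body in the same edit.

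The cost is small. One sentence changes, the reviewers already exist, and IRB reporting continues, although any comparative results would now have to come from the reviewers themselves. The real downside is that the investigators do not see interim results and, after a stop, wait for the remaining follow-up of up to 90 days before they do.

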**g. Withdrawal of Subjects**

Subjects will be withdrawn from the study if they experience an adverse drug reaction defined as anaphylaxis. Other potential side effects such as nausea, vomiting, or diarrhea will be treated symptomatically per standard of care. If refractory to standard treatment for these side effects, subjects will be withdrawn from the study. Subjects experiencing any thrombotic event prior to completion of study drug dosing schedule will be withdrawn from study. Subjects may choose at any time to voluntarily withdraw from the study. If subjects choose to withdraw, their data will not be included for analysis if they did not complete the proposed dosing regimen.

The primary investigator may remove a subject at any time from this research study if it is felt to be in the best interest of the subject.

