**8. Study Design:**

a. Recruitment Methods

Potential subjects will be recruited at their preoperative office visit with their surgeon or, if applicable, during their inpatient stay prior to surgery. Informed consent will be obtained by the Spectrum Health Oncology Research staff. The potential subjects include all patients scheduled to undergo major oncologic surgery that meet all of the

inclusion criteria, and none of the exclusion criteria. There will be no payment to study subjects. We plan to enroll a total of 200 subjects, unless planned interim analyses determine otherwise.

b. Inclusion Criteria

- Subjects undergoing major oncologic surgery for standard of care purposes (to include, but not limited to: liver resections, radical cholecystectomy, pancreaticoduodenectomy (Whipple procedure), esophagectomy, gastrectomy, colectomy, and debulking with hyperthermic intraperitoneal chemotherapy, prostatectomies, nephrectomies, and partial nephrectomies)
- Male or female  $\geq$  18 years of age
- Subject agrees to participate in this study and provides informed consent

Exclusion Criteria

- Subjects with a history of hypercoagulopathy, deep vein thrombosis or pulmonary embolism
- Subjects that are on anticoagulation or antiplatelet medications at the time of surgery other than Aspirin
- Subjects with a history of TIA or Stroke
- Subjects with a history of atrial fibrillation
- Subjects with a known thrombus
- Baseline creatinine level greater than 2.83 mg/dL
- Subjects with known hypersensitivity to tranexamic acid
- Adults unable to provide informed consent
- Children
- Pregnant women
- Prisoners
- Non-English speaking subjects
- Any other medical condition including mental illness or substance abuse deemed by the investigator to be likely to interfere with a subject's ability to provide informed consent, cooperate and take part in this research study

c. Study Endpoints

The primary outcome measures will be operative blood loss and transfusion rates in subjects undergoing the eligible procedures. Secondary outcome measures will include cost of hospitalization, intensive care unit length of stay, and total hospital length of stay.

d. Procedures Involved in the Research

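### Section 8.g withdraws subjects from the whole study for anaphylaxis or refractory symptoms, although with a single pre-surgery infusion this mostly stops no drug and only ends the 90-day follow-up

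*Combined protocol and SAP*

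**What the plan says.** Section 8.g sets three withdrawal triggers that do not depend on the subject's choice:

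- Anaphylaxis: "Subjects will be withdrawn from the study if they experience an adverse drug reaction defined as anaphylaxis".
- Nausea, vomiting or diarrhea that does not respond to treatment: "If refractory to standard treatment for these side effects, subjects will be withdrawn from the study".
- Early thrombosis: "Subjects experiencing any thrombotic event prior to completion of study drug dosing schedule will be withdrawn from study".

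Each removes the subject from the study, not only from study drug. The one sentence in 8.g that excludes data from analysis covers a different group: subjects who choose to withdraw and had not finished dosing.

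Section 8.d (Procedures Involved in the Research) describes a single administration: "The tranexamic acid group will receive a 1000 mg dose immediately preceding surgery, administered by the anesthesiologist". On its duration: "Both the tranexamic acid and placebo will be administered via intravenous piggyback over 15 minutes". No later dose is described. On follow-up: "Subjects will be followed for 90 days postoperatively". The postoperative data listed there are hemoglobin, transfusion, complications, thromboembolic events, ICU and hospital stay, cost and readmission.

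Section 8.c makes transfusion part of the primary outcome: "The primary outcome measures will be operative blood loss and transfusion rates in subjects undergoing the eligible procedures". Section 8.f provides for safety recording: "Adverse events including thromboembolic events and development of acute renal failure will be monitored and recorded on a weekly basis by study personnel". Section 9.a counts eligible, consenting subjects who complete dosing. Section 9.b gives no method for missing data.

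**The concern.** The withdrawal rule reads as though a course of drug were being given, so that taking a subject out would spare further exposure. Under 8.d there is normally no further exposure to spare. The protocol never separates ending study drug from ending observation, so a rule that looks like a treatment rule works as a follow-up rule.

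The trigger occurs after randomization, and 8.g itself classes it as a potential side effect. Subjects who leave this way are therefore not a random subset, and their number may differ by arm. What would go missing is the postoperative part of the transfusion outcome, all of the secondary outcomes (cost, ICU stay, hospital stay), and thromboembolic events after the withdrawal date. The last matters because 8.f makes the trial's continuation depend on comparing adverse events between arms. The interim reviews in 8.f are also timed by subjects completing the study, and the documents do not say whether a withdrawn subject counts.

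**Working it through.** **Step 1. What withdrawal stops, trigger by trigger (8.g against 8.d).**

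- *Refractory symptoms.* The symptom must appear, be treated, and fail to respond. The infusion lasts 15 minutes and directly precedes surgery, so this sequence would normally finish after dosing has ended. Withdrawal stops no drug; what remains to be stopped is follow-up.
- *Anaphylaxis.* It may occur during the 15 minutes, when stopping the infusion is a real action. Leaving the 90-day follow-up is a separate step that does not follow from it.
- *Thrombotic event before dosing is complete.* With a single infusion the window closes when that infusion ends, so few subjects can qualify.

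**Step 2. What is kept and what is lost.** Operative blood loss and intraoperative transfusion come from the operative record and would normally exist before symptoms are called refractory. Section 9.a counts subjects who completed dosing, which these subjects did. Section 8.f would still record the triggering event. The loss is therefore of data after the withdrawal date. An infusion interrupted by anaphylaxis or thrombosis is different: that subject may also fall outside the set of completers in 9.a.

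**Step 3. Size.** The documents give no withdrawal rate. Assume a fraction w = 2%, 5% or 10% of the planned 200: 200 × w = 4, 10 or 20 subjects without full 90-day data.

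*The plan's own figure.* The 200 is not in dispute here. It cannot be uniquely reproduced, because control rate and power are not stated. One set of assumptions that gives it is 25% against 10% transfused, two-sided 0.05, 80% power: 100 per arm.

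*Power.* Assume 40% against 20% transfused (a 20-point absolute reduction), two-sided 0.05, and the pooled-variance formula

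power = Φ{[|p1 − p2|√n − 1.96√(2p̄(1 − p̄))] / √[p1(1 − p1) + p2(1 − p2)]}.

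At n = 100 per arm: (2.000 − 1.270)/0.632 = 1.154, power 0.876. At n = 98, 95 and 90: 0.869, 0.859 and 0.839. The loss of power is small.

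*Possible error in one arm's transfusion rate.* Let p be the rate among observed subjects and q the unknown rate among the fraction w withdrawn. The true rate is (1 − w)p + wq, so the error is w(q − p), which lies between −wp and w(1 − p). With p = 20% (assumed):

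| w | lower limit | upper limit |
|---|---|---|
| 2% | −0.4 points | +1.6 points |
| 5% | −1 point | +4 points |
| 10% | −2 points | +8 points |

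These are outer limits, because some withdrawn subjects will already have a recorded intraoperative transfusion. For scale, 9.a anticipates a 15-20% reduction, without saying whether this is absolute or relative.

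**The case against.** The strongest reply is that loss of data is inferred from silence. Section 8.g excludes data only for subjects who choose to withdraw before finishing dosing; 9.a keeps those who finished; 8.f records adverse events weekly and does not exempt an event that causes withdrawal. This stands as far as it goes. A reader might infer that the rule deletes the data already collected on these subjects, or hides the reactions themselves; the documents support neither. It does not answer the point about later data: withdrawal from the study, followed as written, ends collection, and no provision says otherwise.

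A reader might also infer that the rule makes tranexamic acid look safer and cheaper. The documents do not support a direction. Gastrointestinal symptoms can also follow the eligible operations, in both arms, and no difference between arms is shown.

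A large missed safety signal is equally tempting. If 5%, 10% or 15% of 200 were withdrawn, with a 10% thromboembolic risk against 5% in the rest and every event falling after withdrawal, then 1 of 10.5, 2 of 11 or 3 of 11.5 expected events would be missed (10%, 18%, 26%). The arithmetic is right, but no input has a source. With equal risks the shares are simply 5%, 10% and 15%, and since both arms are pooled they do not describe a between-arm signal.

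Finally, the withdrawal text is the only wording that could imply stopping an infusion in progress, so it should not simply be deleted. That is accepted and shapes the remedy.

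**Conclusion.** The point holds as a limited, inexpensive improvement. The two triggers that matter, anaphylaxis and refractory symptoms, end study participation. For refractory symptoms this normally spares no drug and costs the remaining 90-day data. The thrombotic clause adds little under a single infusion.

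The number affected is unknown and probably small. Power is not the issue. The issue is loss that is not at random with respect to a possible drug effect, of unknown direction, bounded for one arm by the limits shown above under assumed withdrawal of 2-10% and a 20% observed transfusion rate. The conclusion rests on two readings: that withdrawal from the study means observation ends, and that 8.d describes the complete dosing.

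**What to change.** In section 8.g, separate stopping study drug from leaving the study. Leave any rule on stopping the infusion, and on clinical care, as the sponsor sets it. Then state that subjects who meet these protocol-driven criteria have the event recorded and continue outcome and safety data collection to day 90 unless they withdraw consent.

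Reconcile the references to a dosing schedule and a dosing regimen in 8.g and 9.a with the single infusion in 8.d. State whether a subject whose infusion was interrupted by such an event stays in the analysis; amending 8.g alone would leave the completion condition in 9.a in force. It would also help to say whether withdrawn subjects count towards each block of 50 in 8.f.

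The cost is an amendment to 8.g with a matching clarification in 9.a, and slightly more follow-up for a probably small number of subjects. Sections 8.d to 8.f already provide for collecting these data.

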## **9. Statistical Plan**

### **a. Sample Size Determination**

We anticipate a 15-20% reduction in transfusion rates in the tranexamic arm when compared with placebo treatment. A sample size of 200 total subjects, 100 in each arm of the study, will be required to obtain a statistically significant result with  $p <0.05$ . Randomization will ensure an equal number of respective surgeries between the treatment and placebo arms of the study. All subjects who consent to the trial who meet the above inclusion criteria and complete the proposed dosing regimen will be included in the sample size.

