**5. Background:**

Tranexamic acid was first introduced in the 1960's as a treatment for heavy menstrual bleeding. This medication inhibits fibrinolysis by inhibiting multiple plasminogen binding sites. In the past two decades, its use has been incorporated into surgical practice for patients undergoing open-heart surgery, liver transplantation, and urologic surgery. Recent reports of decreased mortality in patients with traumatic hemorrhage receiving tranexamic acid have shown significant promise. A 2006 study published out of Taiwan demonstrated decreased blood loss, reduced transfusion rates, and decreased overall hospital cost in patients undergoing liver resections for both benign and malignant conditions.

Major oncologic surgeries involving the liver and gastrointestinal tract involve extensive dissection, which can result in significant operative blood loss requiring intra- or postoperative transfusion. Tranexamic acid may be a useful addition in procedures with significant blood loss, as previous studies indicate it is both safe and affordable. While reports of seizure activity have been published when used at high doses (100 mg/kg), standard dosing regimens have proven to be safe and effective. The beneficial effect of reduction in bleeding has been demonstrated without an increase in thromboembolic events. We believe tranexamic acid has potential to reduce bleeding in major oncologic surgery resulting in reduced blood loss and lower transfusion rates. An improvement in the rate of surgical complications related to bleeding may also result in decreased hospital costs as well.

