**7. Resources Available to Conduct this Research:**

Approximately 15 major oncologic surgeries are performed on a monthly basis at the Spectrum Health Butterworth Campus. All individuals scheduled to undergo these surgeries that meet the eligibility criteria will be recruited for enrollment. Study personnel will include surgical residents with experience in surgical oncology research and knowledge of surgical outcome measures, with monitoring by a staff surgical oncologist.

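### Are 200 subjects too few for the 15-20% reduction in transfusion that Section 9a anticipates?

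*Combined protocol and SAP*

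**What the plan says.** The whole justification is in Section 9a. The expected effect is "We anticipate a 15-20% reduction in transfusion rates in the tranexamic arm when compared with placebo treatment", followed by "A sample size of 200 total subjects, 100 in each arm of the study, will be required to obtain a statistically significant result with" p below 0.05. The section adds that eligible, consenting subjects who "complete the proposed dosing regimen will be included in the sample size".

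Section 8a gives the same total as an enrolment target: "We plan to enroll a total of 200 subjects, unless planned interim analyses determine otherwise". Section 8g says of subjects who choose to withdraw that "their data will not be included for analysis if they did not complete the proposed dosing regimen". Section 9b assigns the chi-square test to nominal variables, at p<0.05. Section 8c names two primary outcomes, operative blood loss and transfusion rates; only transfusion appears in the sizing paragraph.

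No section gives a placebo transfusion rate, a power, whether the test is one- or two-sided, or whether 15-20% is relative or in percentage points. On how common transfusion is, Section 5 says only that the dissection is extensive, "which can result in significant operative blood loss requiring intra- or postoperative transfusion".

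**The concern.** A percentage reduction compared with placebo can be read as a relative reduction. On that reading a fall of 20% from a 40% control rate is 40% to 32%; in percentage points it is 40% to 20%. The required sizes differ several-fold. If relative was meant, 200 people would enter a transfusion comparison that misses its own anticipated effect in 60-92% of repetitions at control rates of 20-60%, and a non-significant result would tell the reader little.

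Two lesser points add to the impression. The total of 200 is enrolled in Section 8a, while Section 9a counts only those who complete dosing, so nothing is held in reserve. The unblinded reviews "after every 50 subjects complete the study" have no stated control rate or target difference beside them.

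**Working it through.** **Inputs.** From the plan: 100 per arm and a 15-20% reduction (Section 9a); chi-square test at p<0.05 (Section 9b). Assumed, because the plan is silent: two-sided test, 80% power as the benchmark, a single analysis, control rates from 20% to 60%.

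**Formulas** (pooled variance; p1 control, p2 treated, d = p1 − p2, p̄ their mean):

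- n per arm = [1.960·√(2p̄(1−p̄)) + 0.842·√(p1(1−p1)+p2(1−p2))]² / d²
- power = Φ{[d·√n − 1.960·√(2p̄(1−p̄))] / √(p1(1−p1)+p2(1−p2))}

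**1. The plan's own figure.** It cannot be derived from stated inputs, but it can be matched. For 25% v 10%: (1.0532 + 0.4434)² / 0.0225 ≈ 99.5, so 100 per arm. Twenty points from 50-60% needs 93-97 per arm; 15 points from 20% at 90% power needs 101.

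**2. Both readings.** Needed per arm at 80% power, then power with 100 per arm:

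| Control rate | n: 20 / 15 points | Power: 20 / 15 points | n: relative 20% / 15% | Power: relative 20% / 15% |
|---|---|---|---|---|
| 20% | – / 76 | – / 90.0% | 1,447 / 2,629 | 11.0% / 7.9% |
| 25% | 49 / 100 | 98.1% / 80.2% | 1,094 / 1,984 | 13.2% / 9.1% |
| 30% | 62 / 121 | 94.8% / 72.2% | 859 / 1,554 | 15.7% / 10.5% |
| 40% | 82 / 152 | 87.6% / 62.1% | 564 / 1,016 | 21.6% / 13.9% |
| 50% | 93 / 170 | 82.8% / 57.4% | 388 / 693 | 29.4% / 18.4% |
| 60% | 97 / 173 | 81.2% / 56.6% | 270 / 478 | 39.8% / 24.8% |

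One relative case in full, 40% to 32%: (1.3305 + 0.5693)² / 0.0064 ≈ 563.9, so 564 per arm.

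The lowest power for a 20-point fall is at 60% v 40%: Φ{(2.000 − 1.386)/0.693} = Φ(0.886) = 81.2%.

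A relative reduction reaches 80% power with 100 per arm only if about 84% (20% reduction) or 92% (15% reduction) of placebo subjects are transfused. Within 20-60%, even a one-sided test needs at least 213 per arm.

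**3. The sentence taken literally.** Section 9a speaks of obtaining a significant result, not of power. The standard error of the difference is largest at p̄ = 0.5: √(2 × 0.25/100) = 0.0707. An observed 15-point difference then gives z = 0.15/0.0707 = 2.12, p = 0.034. With a continuity correction, z = (0.15 − 0.01)/0.0707 = 1.98, p = 0.048. So 15 observed points with 100 per arm are significant at any control rate. This is weaker than having power for a true 15 points.

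**4. Incomplete dosing.** For 25% v 10%, power is 80.2% with 100 per arm, 78.1% with 95 and 75.9% with 90. Restoring 100 analysed per arm means 100/0.95 → 106 (212 in all) or 100/0.90 → 112 (224 in all).

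**5. Time.** Section 7 says: "Approximately 15 major oncologic surgeries are performed on a monthly basis". With every patient enrolled, 200/15 = 13.3 months. The worst percentage-point case needs 2 × 173 = 346 subjects, or 346/15 = 23.1 months. The relative reading at 40% control needs 1,128/15 = 75 to 2,032/15 = 135 months.

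**6. The other primary outcome.** For blood loss by t-test, 100 per arm gives 80% power for a difference of (1.960 + 0.842) × √(2/100) = 0.40 SD. The low-power figures above do not apply to it.

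**The case for a change.** The strongest case for a change is that the plan never says which effect was meant, and one of the two readings leaves the trial without useful power for transfusion. Choosing percentage points because it makes 200 come out right assumes that the calculation was sound. Even then, a 15-point fall has 80% power only at control rates up to about 25% (or from about 90%), and no rate is given. A sentence naming the control rate, power, sidedness and scale would cost almost nothing.

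The description stands: Section 9a is incomplete and 200 cannot be re-derived from it. The inference to a defective design does not. The wording allows either scale, since transfusion rates are themselves percentages, and the only internal evidence, the number 200, fits percentage points and is far from the relative reading at any control rate from 20% to 60%. The 8-40% power and 60-92% miss rate need both the less likely reading and assumed control rates.

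The lesser points are small. Dosing is one 15-minute infusion immediately before surgery (Section 8d), so few subjects should be lost part-way, and a 5-10% loss costs 2-4 points of power. Section 8f describes the reviews as looking for statistically significant findings, not as re-estimating the sample size, and the clause in Section 8a fits early stopping. A confidence interval for the difference can be rebuilt from two percentages and the arm sizes.

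**Conclusion.** The concern does not call for a change. The justification is thin, but no calculation in it is shown to be wrong, and it states no power that the design fails to reach. In percentage points, the reading that the stated size supports, 100 per arm has at least 81% power for a 20-point fall at any control rate, and 80% or more for a 15-point fall at control rates up to 25%.

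What remains is lower power at the bottom of the anticipated range: 72% for 15 points at a 30% control rate, and about 57% at 50-60%. Covering that case could take 346 subjects and about 10 more months at best at this site, against a control rate that nobody has stated. Accepting 200 is a fair trade-off. Filling in Section 9a would improve the record, but it would not alter who is enrolled, what is measured or how the arms are compared.

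This rests on a two-sided 5% test, a single analysis and the percentage-point reading. If a relative reduction was truly intended, 200 would be inadequate unless about 84-92% of placebo subjects are transfused, and nothing in the documents points to rates that high. The effect of repeated interim testing on the error rate is a separate question and is not settled here.
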